11.2.3 Additional analysis

Not applicable

11.2.4 The level of significance

A p-value less than 0.05 was considered significant and was denoted by *.

11.2.5 Analysis Population

The outcome of this single arm clinical trial is compared with other clinical trials and our previous retrospective neoadjuvant chemoradiation data of CGMH.

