Using multiplex immunohistochemistry, we will comprehensively characterize immune cell infiltration patterns, including CD4+ and CD8+ T cells, regulatory T cells (Tregs), macrophages (M1 and M2 phenotypes), and dendritic cells, as well as assess expression levels of immune checkpoint molecules such as PD-1, PD-L1, CTLA-4, and CD47 on both immune and tumor cells. We will also evaluate stromal components, cytokine-associated markers, and markers of tissue damage or repair to assess treatment-induced changes in both tumor and normal mucosa. By comparing immune cell composition, activation states, and checkpoint expression in tissues from curcumin-treated versus untreated cohorts, we aim to delineate how curcumin modulates the immunological landscape of CRC. This will help determine whether curcumin not only amplifies local and systemic antitumor immunity but also confers a protective effect against treatment-induced inflammation and injury in adjacent normal tissues [25].

5. Study Population

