5.1 Inclusion Criteria

Treatment group

Inclusion criteria:

- (A) Males and females more than 20 years of age
- (B) Signed informed consent
- (C) Patients with a pathologically proven rectal adenocarcinoma located less than 10 cm to the anus.

- (D) Clinical staging (AJCC 8th ed.): T2-4 N0 M0 or T any N1-2 M0
- (E) Distal metastasis has been excluded by imaging study: by chest-to-pelvic computed tomography or Positron Emission Tomography
- (F) Preoperative pelvic staging by pelvic Magnetic Resonance Imaging (preferred) or trans-rectal ultrasound
- (G) Patients with WHO/ECOG performance scale 0 or 1

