5.2 Exclusion Criteria

Treatment group

Exclusion criteria:

- (A) Refuse to sign the informed consent
- (B) Distal metastasis revealed by the imaging study
- (C) Patients does not receive radiotherapy
- (D) Unable to receive further curative resection
- (E) Patients receive tumor resection before the neoadjuvant treatment
- (F) Patients have history of more than 5 Gy of pelvic radiation
- (G) Patients in pregnancy or lactation status
- (H) Patients have allergic history to curcumin, 5-fluouracil or oxaliplatin
- (I) Patients of childbearing potential can not cooperate with appropriate contraceptive method (oral, injectable, or implantable hormonal contraceptive; tubal ligation; intra-uterine device; barrier contraceptive with spermicide; or vasectomized partner)
- (J) Patients with any concurrent malignancy; patients with history of malignancy should be cancer-free for more than 5 years
- (K) Patients with New York Heart Association (NYHA) class III or IV heart failure, unstable angina pectoris, unstable cardiac arrhythmia or tachycardia (heart rate > 100 beats/minute)
- (L) Patients have concurrent uncontrolled medical conditions, such as illness ongoing or requiring IV antibiotics, severe chronic renal failure (eGFR <30 mL/min/1.73m²) or severe active hepatitis(AST/ALT>3x upper normal limit) ` Total Bilirubin>2 mg/dl...etc.
- (M) Patients with previous or current drug abuse
- (N) Patients underwent major surgery within 28 days of study enrollment (except diverting colostomy)
- (O) Patients have Familial Adenomatosis Polyposis Coli (FAP), Hereditary Non-Polyposis Colorectal Cancer (HNPCC), active Crohn's disease or active ulcerative Colitis
- (P) Patients have known dipyrimidine dehydrogenase deficiency (DPD)
- (Q) Patients with congenital iron metabolic or hematopoietic diseases
- (R) Patients with synchronous colon cancer
- (S) The Patients with hematologic abnormalities (INR > 1.5, white blood cell (WBC) count < 3,000/ μ L, absolute neutrophil count (ANC) < 1,500/ μ L, platelet count <**

100,000/ μ L, hemoglobin < 9.0 g/dL not caused by tumor treatment) or known hematologic diseases (aplastic anemia, myelodysplastic syndrome (MDS), leukemia, malignant lymphoma, multiple myeloma, hereditary hematologic diseases such as thalassemia, sickle cell anemia, etc.).

(T) The patient has diabetes mellitus

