(U) The patient is taking the immunosuppressants Cyclosporine, Tacrolimus, Sirolimus, and Everolimus and Everolimus and anticoagulants (warfarin、NOACs、aspirin)

(V) Patients with The medical, psychological, or social condition that, in the opinion of the investigator, may increase the patient's risk or limit the patient's adherence with study requirements

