5.3 Withdrawal criteria

Subject should be withdrawn from the study due to any of the following conditions:

1. The subject voluntarily decides to withdraw her/his consent
2. The subject dies or is lost to follow-up
3. The subject is pregnancy
4. The subject develops disease progression (metastasis or enlargement confirmed)
5. Any clinical adverse event, laboratory abnormality, intercurrent illness, or any occurrence or change in the subject's physically and/or psychologically status giving indication to the investigator that further participation in the study may not be the best interest of the subject
6. The subject does not receive, or is unable to receive, the study intervention, does not keep appointments, or otherwise does not adhere to protocol requirements
7. The subject was enrolled by error and/or it is discovered that the subject does not meet the eligibility criteria after enrollment
8. The study is terminated prematurely by the investigator, research institution, sponsor, IRB or regulatory authorities

For a subject who is withdrawn due to progress confirmed, CT (or MRI) and colonoscopy could be waived at the Early Termination Visit per the investigator's judgments. If a subject is discontinued due to an AE, every effort will be made to follow the event until event resolves or stabilizes at a level acceptable to the investigator.

6. Treatments

6.1.Treatment Administration

A daily dose or high bioavailability curcumin (BCM-95 curcumin) 3g per day is given orally along with the neoadjuvant short-course radiation therapy and chemotherapy.

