1.3 UFUR (one cycle)

*Tegafur 300-350 mg/m²/day and leucovorin 90mg/day PO on day 1 to day 5, then rest for 2 days for 2 weeks

1.4 The radiation therapy modules are as follows:

Short-Course (hypofractionated, 25 Gy/5 fractions) Radiotherapy (SCRT)

2. Prohibited Therapy : cell therapy, immunotherapy

7. Efficacy Assessments

1. **Grade 3 enteritis/proctitis**: evaluated by National Cancer Institute Common Terminology Criteria for Adverse Events Version 5.0 (NCI CTCAE v. 5.0) and the criteria of the Radiation Therapy Oncology Group (RTOG) and European Organization for Research and Treatment of Cancer (EORTC). The sign or symptoms of radiation proctitis (diarrhea, rectal bleeding, rectal pain) is evaluated and recorded by our research nurse 2 to 4 weeks after radiation therapy completed. Colonoscopy evaluation for Vienna Rectoscopy Score will take place 2 to 3 weeks after the radiation therapy is completed.
2. Any grade III adverse events during the neoadjuvant therapy: evaluated by clinicians according to National Cancer Institute Common Terminology Criteria for Adverse Events Version 5.0 (NCI CTCAE v. 5.0) every cycles of chemotherapy. An additional evaluation and record will be recorded by the research nurse every 3 cycles of chemotherapy.
3. Clinical complete response rate of the primary tumor after completion of the neoadjuvant treatment: evaluated by Response Evaluation Criteria in Solid Tumors Version 1.1 (RECIST v1.1) after neoadjuvant chemotherapy and radiation therapy completed
4. Pathological or clinical complete response rate of the primary tumor after completion of the neoadjuvant treatment: defined as no residual cancer cells in the resected specimen after curative resection
5. Patient's tolerability and completion rate of the neoadjuvant therapy

8. Safety Assessments

The complete blood count is evaluated on each admission for chemotherapy. The adverse events is evaluated according to National Cancer Institute Common Terminology Criteria for Adverse Events Version 5.0 (NCI CTCAE v. 5.0). Serum creatinine, electrolyte, AST, ALT, total and direct bilirubin is examined on each 3 cycle of chemotherapy.

If ALT or AST exceeds three times the upper limit of normal (3×ULN), curcumin administration will be suspended. This 3×ULN threshold is a commonly used warning indicator for drug-induced liver injury. In such cases, we will monitor liver function tests weekly until the values recover to <1.5×ULN or return to baseline.

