11.2 Planned Statistical methods of analysis

Categorical variables were compared using Pearson's chi-squared test or Fisher's exact test, while continuous variables were compared using the Mann–Whitey U test. Survival curves were generated using the Kaplan–Meier method and compared between the two groups using the log-rank test. The index date of survival analysis was the day the patient started radiotherapy. All statistical analyses were performed using the Statistical Package for Social Sciences (SPSS), version 24 (IBM Corp., New York, NY, USA). Differences were considered statistically significant at a two-sided p-value of < 0.05 .

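### The external comparator in 11.2.5 has no stated eligibility, regimen, period or grading rule and is tested without adjustment, so case mix or ascertainment can pass for a curcumin effect or hide one

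*Protocol*

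**What the plan says.** Protocol 11.2.5, headed Analysis Population, contains a single sentence: "The outcome of this single arm clinical trial is compared with other clinical trials and our previous retrospective neoadjuvant chemoradiation data of CGMH". It names no trial. For the hospital series it gives no calendar period, eligibility, radiotherapy or chemotherapy regimen, or method of grading toxicity.

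The tests in sections 11 and 11.2 are the t-test, Mann-Whitney, chi-squared or Fisher, and survival curves "compared between the two groups using the log-rank test". None is adjusted, and 11.2.3 lists no additional analysis. The tumour-biopsy text under 4.3 also plans a comparison "in tissues from curcumin-treated versus untreated cohorts", without defining the untreated cohort.

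The eligibility lists in 5.1 and 5.2 are headed as applying to the treatment group, and no comparator list follows. Among the exclusions are "The patient has diabetes mellitus", use of warfarin, NOACs or aspirin, INR above 1.5 and low blood counts. ECOG must be 0 or 1.

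Under 6.1 curcumin "is given orally along with the neoadjuvant short-course radiation therapy and chemotherapy". The run-in cohort in 4.1 instead lists long-course radiotherapy (50.4 Gy in 28 fractions) with capecitabine. Section 7 has a research nurse record proctitis signs, including rectal bleeding, 2 to 4 weeks after radiotherapy, with colonoscopy at 2 to 3 weeks.

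The sample size (4.2 and 11.1) uses a different framework: a one-sample exact test of 30% against 15%, with 64 evaluable and 72 enrolled patients.

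**The concern.** In a single-arm trial the external comparator does the work of a control arm, so its definition is a design decision. Here it is left open in four ways that bear on the result.

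- **Case mix.** Excluding anticoagulant and aspirin users and patients with raised INR bears directly on rectal bleeding, which is one of the assessed proctitis signs. If the comparator is not filtered in the same way, the trial arm may have a lower event rate without any drug effect.
- **Ascertainment.** A nurse assessment in a fixed window and a scheduled colonoscopy can find events that retrospective records miss. This works against curcumin.
- **Regimen.** No fractionation or chemotherapy is required of the comparator, so it may or may not match 6.2.
- **Choice after the fact.** Unnamed trials, and a series with no fixed patient list, allow the comparison to be selected once results are known.

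An inert product could therefore look protective, or a useful one look inert, and the planned unadjusted tests would not separate either from a true effect. The protocol also leaves unclear whether the primary conclusion rests on the fixed 30% or on this cohort.

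**Working it through.** **1. The plan's own figure.** Inputs from 11.1 and 11.2: p0 = 0.30, p1 = 0.15, 80% power, two-sided 5%, 10% drop-out. The normal approximation gives

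n = [(1.960 × √(0.30 × 0.70) + 0.842 × √(0.15 × 0.85)) / 0.15]² = 63.86, rounded up to 64.

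64 / 0.90 = 71.1, rounded up to 72. Both stated figures reproduce. The calculation uses only the fixed 30%; the comparator of 11.2.5 does not enter it.

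**2. Decision rule at 64 patients.** For the exact test with a 2.5% lower tail at p0 = 0.30, P(X ≤ 11) = 1.45% and P(X ≤ 12) = 2.99%. Success is therefore declared at 11 or fewer events.

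**3. How far selection might move the background rate (assumption).** The protocol gives no rate for eligible patients without curcumin. Suppose an unselected series has a 30% rate, a fraction f of it would fail 5.2, and those patients have RR times the risk of the others. The rate in eligible patients is then 0.30 / [(1 − f) + f × RR].

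- f = 0.2, RR = 1.5: 0.30 / 1.10 = 27.3%
- f = 0.2, RR = 2, or f = 0.4, RR = 1.5: 0.30 / 1.20 = 25.0%
- f = 0.4, RR = 2: 0.30 / 1.40 = 21.4%

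**4. Chance of declaring benefit when curcumin does nothing**, P(X ≤ 11 | n = 64, true rate):

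| True background rate | False benefit |
|---|---|
| 30% | 1.5% |
| 27.3% | 4.2% |
| 25% | 9.3% |
| 21.4% | 26% |

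The mild end exceeds the 2.5% tail but stays below 5%; the other end is about ten times that tail. The table describes the one-sample test of 11.1, not the comparison in 11.2.5.

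**5. The same question for a two-group comparison (assumed sizes).** Take 64 trial patients against a historical series at 30% with 64 to 300 patients, an unadjusted pooled z-test and a 2.5% tail. With no drug effect, benefit is declared with probability 2.3-2.6% if the trial population's background is also 30%, 9-11% if it is 25%, and 26-36% if it is 20%. The size and rate of the series are assumptions, because 11.2.5 gives neither.

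**6. What arithmetic cannot settle.** Steps 3 to 5 model selection alone. Closer ascertainment in the trial arm would raise its observed rate and pull the other way. The documents give no figure for that, so no net bias can be calculated.

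**The case against.** Historical comparison is inherent in a single-arm phase II trial, and filtering, matching and adjustment are often set out in a statistical analysis plan, which may exist here unseen. That is fair for the modelling details. It does not cover the choice of comparator, which the protocol addresses in its own section and leaves open.

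Several stronger readings are tempting, and the documents do not support them.

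- A reader might infer that the comparator is unrestricted and contains the diabetic and anticoagulated patients whom the trial excludes. The protocol only states no restriction, and the synopsis gives the same criteria without the treatment-group heading.
- A reader might take chemoradiation to mean that the hospital series was long-course. The protocol uses the same word for its own course in the synopsis and 4.1, so a regimen difference is possible but not shown. The regimen conflict that is on the page lies within the trial itself, between the run-in in 4.1 and 6.1-6.2.
- A reader might argue that admitting T2 N0 patients inflates complete response against a more advanced series. Nothing describes the stage of the hospital series.
- A reader might treat the false-benefit table as the error rate of the 11.2.5 comparison. It belongs to the fixed-30% test, and restricting the hospital cohort would not alter it unless the 30% were also replaced. For proctitis, that fixed 30% also limits how far the benchmark could be chosen afterwards.

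**Conclusion.** The point holds as a defect in how the comparator is specified. Following 11, 11.2 and 11.2.5 as written, a difference between the trial arm and the external sources could not be attributed to curcumin, nor could the absence of one be read as lack of effect. The net direction of bias is unknown: selection may favour curcumin, closer ascertainment may count against it, and the part played by regimen cannot be judged.

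The size is illustrative only. Under assumed background rates of 21.4% to 27.3%, false benefit in the fixed-30% exact test ranges from 26% down to 4.2%, against 1.5% when the background really is 30%. These figures rest on the assumed ineligible fraction (20-40%) and risk ratio (1.5-2), neither of which is in the protocol. The need to define the comparator in advance does not depend on them.

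**What to change.** Rewrite 11.2.5 and the related text in 11.2 as follows.

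1. Limit the hospital comparator to patients who meet 5.1 and 5.2 as far as their pre-treatment records allow, and who received the trial's regimens. The run-in text in 4.1 must first be reconciled with 6.1-6.2 so that those regimens are unambiguous.
2. Take toxicity from the same window after radiotherapy as in section 7.
3. For this comparison, replace the unadjusted tests with one adjusted or weighted for T/N stage, age and chemotherapy regimen.
4. Freeze the comparator's patient list and event rate before any trial outcome is tabulated.
5. State whether the primary test is against the fixed 30% or against this cohort.
6. Name any published trials now, as descriptive context only.

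The cost is protocol wording and a filtered chart extraction from data the sponsor says it has. The filtered cohort will be smaller, possibly too small for more than description, and the documents do not show how many matching patients exist or whether their toxicity can be graded in that window. The benchmark may also prove less favourable than 30%.

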11.2.5.1 Procedure for accounting for missing, unused and spurious data

The incomplete clinical data and sequencing data with poor quality will be excluded in the study.

11.2.5.2 Procedures for reporting any deviation(s) from the original statistical plan

Investigators permit IRB to access to the raw data of experiment for trial-related monitoring, audits and regulatory inspection if additional statistical plan is required.

12. Direct access to source data/documents

Investigators permit IRB to access to the source data of experiment for trial-related monitoring, audits and regulatory inspection.

13. Ethical considerations

This study will be conducted according to Taiwan and international standards of Good Clinical Practice for all studies. Applicable government regulations and Chang Gung Medical Foundation research policies and procedures will also be followed.

This protocol and any amendments will be submitted to the Chang Gung Medical Foundation Institutional Review Board (IRB) for formal approval to conduct the study. The decision of the IRB concerning the conduct of the study will be made in writing to the investigator.

All subjects for this study will be provided a consent form describing this study and providing sufficient information for subjects to make an informed decision about their participation in this study. This consent form will be submitted with the protocol for review and approval by the IRB. The formal consent of a subject, using the IRB-approved consent form, will be obtained before that subject is submitted to any study procedure. This consent form must be signed by the subject or legally acceptable surrogate, and the investigator-designated research professional obtaining the consent.

14. Data handling and keeping

Clinical samples will be collected in Chang Gung Medical Foundation. The sequencing data will be stored in computers of laboratory with an electronic encryption. The clinical and source data can only be assessed by clinical doctors and investigators of the study.

Data and Safety Monitoring Plan (DSMP)

This section outlines the Data and Safety Monitoring Plan (DSMP) for the clinical study. The purpose of the DSMP is to ensure the safety of study participants and the integrity of the study data. The monitoring activities will be performed regularly and will be adapted based on study progress and emerging safety signals.

1. Monitoring Plan

- Enrollment monitoring will be conducted tri-monthly by the Principal Investigator (PI).
- Serious Adverse Events (SAEs) will be reported immediately and reviewed quarterly by the Safety Officer.
- Protocol deviations will be recorded and reviewed monthly by the Clinical Research Coordinator (CRC).
- Data quality will be assessed on an ongoing basis by the Data Manager.

2. Reporting

All safety monitoring activities and findings will be reported to the Sponsor and PI.

15. Financing and Insurance

This study is supported by Chang Gung Medical Foundation (CGMF). The main research fund is aimed to be supported by Chang Gung Medical Foundation.

16. Privacy and Confidentiality Protection

A research code will be used to represent the patient's identity, and this code will not display the patient's name, ID number, or address. The principal investigator will maintain a strict confidentiality stance regarding the results and diagnoses of the patient's visit. If research findings are published, the patient's identity will still be kept confidential.

By signing the consent form, the patient is agree that his or her visit records may be directly reviewed by monitors, auditors, research ethics committees, and regulatory authorities to ensure that the research process and data comply with relevant laws and regulations. The individuals mentioned above also pledge never to violate the confidentiality of the patient's identity.

According to the regulations of the United States or the European Union for pharmaceutical management, trial results will be published on the public clinical trial information website: Clinicaltrials.gov (for the United States). However, the patient's personal information will remain confidential, and the website will only have a summary of the trial results.

17. References

1. Jiao, Y., et al., *Curcumin, a cancer chemopreventive and chemotherapeutic agent, is a biologically active iron chelator*. Blood, The Journal of the American Society of Hematology, 2009. **113**(2): p. 462-469.
2. Imam, Z., et al., *Drug induced liver injury attributed to a curcumin supplement*. Case Reports in Gastrointestinal Medicine, 2019. **2019**.
3. Lao, C.D., et al., *Dose escalation of a curcuminoid formulation*. BMC complementary and alternative medicine, 2006. **6**(1): p. 1-4.
4. Shehzad, A., F. Wahid, and Y.S. Lee, *Curcumin in cancer chemoprevention: molecular targets, pharmacokinetics, bioavailability, and clinical trials*. Archiv der Pharmazie, 2010. **343**(9): p. 489-499.
